**Update: We are in the R33 phase of the study which only has pre- and post treatment scans (2 scans total).**

Subjects who are nicotine smokers and/or caffeine drinkers will be reminded to not smoke or drink caffeine within 2 hours of the MRI scan days and computer task days. Subjects will be asked not to drink alcohol on the day of the task or scan. Users of PRN anti-anxiety medication will be asked to abstain from use on the day of scan unless medically necessary. If a subject does use these substances it will be documented; however they will not be removed from the study.

**Neuroimaging session (at the UNC Biomedical Research Imaging Center (BRIC)):**

All scan sessions will be identical. All patients will receive pre- and post-treatment scans. The first 60 patients enrolled (n=30 who receive BATA and n=30 who receive MBCT) will also receive two mid-treatment 7T fMRI scans approximately 8 and 12 weeks after starting treatment. The 1st phase of the study entered a R61 no cost extension at the end of the project period & due to limited funds, participants will no longer be receiving up to 4 scans. Participants who consent at UNC on or after 11/1/18 will receive only pre- and post-treatment scans (2 scans total). **Update: We are in the R33 phase of the study which only has pre- and post-treatment scans (2 scans total).** Patients who drop out of treatment early before reaching 8 weeks of therapy, will be asked to return for 1 final post-treatment visit to complete the computer tasks, self-report questionnaires, and MRI. They will complete this early termination/post treatment visit all at UNC to reduce the burden on participants to have to return to both Duke and UNC.

Equipment: This study will utilize a research-dedicated Siemens Magnetom 7T whole body MR scanner for MRI data collection.

7T Scan Preparation: After arrival at the BRIC, participants will undergo a final MRI screening prior to the reassessed by the BRIC technologist for any potential contra-indications to the scan. If any concerns are raised, participants will not undergo the scan. If the subject is a female of child bearing potential, she will complete a urine pregnancy test administered by UNC BRIC study personnel. If the test indicates that she is pregnant, the scan will not be done. In either situation (failed checklist or + urine pregnancy screen), subjects will be informed of this decision to cancel the MRI and thanked for their time and will no longer be eligible to continue in the study. Alternatively, if participants are cleared, they will begin out-of-scanner training in preparation for the scan.

All subjects will then be asked about their caffeine, alcohol, nicotine use and sleep habits in the last 24 hours. If female, they will complete the PEERS questionnaire regarding their current reproductive status and answer additional questions about their menstrual cycle. The UNC study team member will then have subjects complete the MID practice task to measure their reaction time. The results from the practice test will be used to calibrate the MID task to the participant's speed level for the MID task in the scanner.

Monetary Incentive Delay (MID) practice run. The practice run is to familiarize them with the computer task and measure reaction time. The results from the practice test will be used to calibrate the MID task to the participant's speed level during the fMRI brain scan.

MRI Scan: After the out-of-scanner training, participants will be escorted to a private room in which they will be asked to change into a pair of clean scrubs provided by the BRIC. They will also be asked to remove any loose objects (e.g., watches, jewelry, cellphones) that may interfere with scanning and secure their belongings in a secured locker only accessible to the participant. A trained BRIC technician will reiterate the requirements for the 7T scan (e.g., remain still, remove jewelry and any other metallic or loose objects) and then assist the participant in entering the MRI scanner. The scan will include the following:

1. Mock Scan
2. Anatomical MRI Scan
3. Resting state fMRI scan

4. Monetary Incentive Delay task (involves pressing a button as quickly as possible to receive a reward)
5. Face- and shape-matching task (involves pressing a button to indicate which two of three faces or shapes match)
6. Perivascular spaces (PVS) sequence known as 3D turbo-spin-echo

Debriefing After the Scan: Upon completion of the 7T fMRI scan, participants will be given time to change back into their own clothing. They will then be escorted back to a separate, private room. At this time, participants will be compensated and will also have the opportunity to ask any questions. At this time the technologist will ask the participant if they experienced any discomfort during the scan to report to the PI, and will tell the participants that this assessment is not meant to constitute a diagnosis.

#### **Treatment (at Duke between 8-15 weeks)**

Patients will complete a course of BATA or MBCT. Subjects will be assigned a specific Duke study therapist and will continue with the same therapist through the 8-15 weeks of therapy. All therapy sessions will occur in Duke CBRTP located in the Civitan building ([name]) or via WebEx/Zoom Duke approved remote platforms. At the end of each therapy visit, the therapist will complete the Clinical Global Impairment scale in relation to improvement of symptoms (CGI-I) and the subject will complete the SHAPS. Starting at the second therapy session, the subject will be asked to give a % of how much of the homework tasks they had completed over the prior week since the last therapy session. The weekly therapy sessions will last around 1 hour, except for weeks 4, 8, 12, and the final therapy session (if not at week 8 or 12) as noted just below. All remote weekly therapy sessions will last around 1 hour.

Weeks 4, 8, and 12 (if applicable) : At these specific therapy visits, subjects will also be asked to complete the EEfRT and PRT computer tasks again. The tasks will be done and the subject will be asked about their caffeine, alcohol, nicotine & sleep habits over the past day in addition to completing SHAPS & % homework tasks completed over the past week (if not already completed during the therapy session). The subject may have their therapy session before or after these tasks & surveys or may be completed on a separate day during the week 4, 8, and 12. The C-SSRS will be administered after the computer tasks. They will then again be asked to complete most of the questionnaires they completed at the screening assessment visit (i.e. R61: the PSWQ, PCL-5, BDI-II, BAI, SF-36, IDAS, TMS, SRS-2, and PhenX measures of related to depressed mood and perceived stress, R33: the MAPS, IDS-RS measures related to anhedonia, BADS, WAI, PSWQ, PCL-5, BDI-II, BAI, SF-36, TMS, and PhenX measures of related to depressed mood and perceived stress). They will complete them directly in REDCap either in-person or by REDCap survey invitation. These visits will last from 2 to 2 ½ hours.

To clarify, computer tasks and REDCap questionnaires will be administered up to 5 times in the study: pre-treatment, 4 weeks 8 weeks, 12 weeks, and post-treatment (if necessary): 1) If the final therapy visit is before week 8, there will be three assessment points (pre-treatment, week 4, and at the last therapy visit); 2) If the final therapy visit is between week 8 and week 12, there will be four assessment points (pre-treatment, week 4, week 8, and at the last therapy visit); 3) If the final therapy visit is after week 12, there will be five assessment points, and post-treatment assessments will be administered at the last therapy session\*. \*\*As noted above, the conduct of the computer tasks with CSSRS at the in-person visit wks 4, 8, 12 and final visit are contingent upon the building availability and approval of in-person visits either at Duke or UNC. If not available and approved, the computer tasks and urine drug screen will be omitted until the study team have the appropriate approvals to do the tasks at an in-person visit. These omissions will not be considered protocol deviations since the omissions are necessary to be able to open the study and begin to collect the main primary outcomes of imaging and therapy.

Final Therapy Visit/Post-Treatment participant characterization:

Duke: At the final therapy visit (anytime between 8-15 weeks as determined by Duke/UNC study team) or separately, the subject will be asked to redo the computer tasks (EEfRT and PRT), complete the SHAPS & % homework tasks 1 last time and then again be asked to complete most of the online questionnaires they completed at the screening assessment visit ((i.e. R61: the PSWQ, PCL-5, BDI-II, BAI, IDAS, SF-36, TMS, SRS-2, PhenX measures of related to depressed mood and perceived stress, R33: the MAPS, IDS-RS measures related to anhedonia, BADS, WAI, PSWQ, PCL-5, BDI-II, BAI, SF-36, TMS, and PhenX measures of related to depressed mood and perceived stress). They will complete them directly in REDCap. Next, the C-SSRS will be done and the subject will be asked a series of questions about feasibility and acceptability of procedures (exit interview), and will be offered referrals for other mental health services as needed. Finally, they will be scheduled for their final fMRI brain scan at UNC. Note: Especially during COVID-19, the final computer tasks, CSSRS, exit interview, and caffeine/alcohol questions may be done at UNC and survey invitation sent out for the REDCap questionnaires. **\*\*Please note that the conduct of the computer tasks with CSSRS at the in-person final visit are contingent upon the building/room availability and approval of in-person visits either at Duke or UNC. If not available and approved, the computer tasks with CSSRS will be omitted until the study team have the appropriate approvals to do the tasks at an in-person visit. These omissions (skipping the in-person visit) will not be considered protocol deviations since the omissions are necessary to be able to open the study and begin to collect the main primary outcomes of imaging and therapy. If omitted, the participant will be emailed the REDCap survey invitation to complete only the self-report with exit interview, as applicable.**

UNC: If the subject's final therapy session occurs between weeks 9-11 or after week 12, they will be scheduled for the final post-treatment MRI and it will occur one last time at the BRIC at UNC. All subjects will be asked about caffeine, nicotine, alcohol, and sleep habits over the past 1 day, if female, have urine pregnancy screen, and then undergo the scan. This visit can last up to 2 hours. As noted, subjects who consented at UNC at 11/1/18 or later, will only have a pre-treatment and a post treatment MRI scan in the 1st phase (R61) and in the R33 phase as per the grant.

Note: If a subject decided before their final scheduled therapy session that they were actually done with therapy and they felt they didn't need to come back for a final session at Duke and the study team agreed, then the subject could do the REDCap self-report, C-SSRS and exit interview at UNC, at their post-treatment MRI visit. This would help reduce the burden on the subject so they would not have to complete 2 separate final visits. It could be done all at 1 time.

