**Endpoints:**

*Primary Endpoints:*

*Imaging (7T) – Tasking based activation to Monetary Incentive Delay (MID) Task; Task based activation to Emotion Reactivity task (Hammer)  
Behavioral/Observational:-Probabilistic Reward Task (PRT) and EffortExpenditure for Reward Task (EEfRT); Changes in SHAPs scores pre/post treatment*

*Secondary & Exploratory Endpoints:*

*Imaging (7T)- Resting state connectivity  
Behavioral/Observational -CGI-I; Homework Completion (participation and clinician-rated); ecological momentary assessment of activation, mood, reward experiences. Passive location tracking (PLT) data via the MetricWire app for the EMA sub-study to compare distance traveled before and after both treatments as a secondary, exploratory measure of behavioral activation. Follow-up analyses will evaluate relations between motion tracking, behavioral, brain, and clinical measures of response to both treatments.*

*PET Aim1: Extract dynamic change in binding potential (BPND%) before, during and after the task and then comparing these values before and after treatment between treatment groups. PET Aim2: Correlations between changes in PET striatal binding potential magnitudes and changes in fMRI.*

Study Population:	This study will recruit participants with clinically significant anhedonia, who are 18-50 years old who are able to read & understand English, and who are seeking treatment.
Phase:	Phase I/II
Description of Sites/Facilities Enrolling Participants:	Recruitment and therapeutic intervention for the study managed by Duke University Medical Center, Department of Psychiatry and Behavioral Sciences and Duke PI ;Eligible participants based on the initial Duke study assessment consent at UNC-Chapel Hill in the Department of Psychiatry under UNC PI for all 7T imaging, EMA and optional PET Scans.

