## 1.3 SCHEDULE OF ACTIVITIES (SOA)

## TIMELINE OF STUDY ASSESSMENTS AND PROCEDURES:

Assessment/Procedure	Online/Phone Screen	Remote/In Person Screen (at Duke) - can be split in 1-2 visits (part remote/part in-person)**	Pre-Tx fMRI (at UNC)	Intervention therapy sessions at Duke) 	Wks 4, 8 & 12 (if applicable) 	fMRI (wk 8 & 12) 	Study Completion Visit-Part I (Duke)	Part II Post-Tx fMRI (UNC)
Online/Phone Screen Questionnaire	X							
Informed consent		X (via Duke REDCap econsent)	X (UNC specific consent)					
SHAPS	X	X	X	X	X	X	X	X
C-SSRS		X			X (post)		X (post)	
SCID5 relevant to inclusion /exclusion, NART		X						
SCID-5-RV		X						
[name] & Background info, CGI-S, CTQ		X						
R61 Phase: BDI-II, BAI, SF-36, PhenX depression & perceived stress, PCL-5, PSWQ, IDAS, TMS, SRS-2		X			X		X	
R33 Phase: BDI-II, BAI, SF-36, PhenX depression & perceived stress, PCL-5, PSWQ, TMS, MAPS, IDS-RS, BADS		X			X		X	
R33 Phase: WAI					X		X	
EEfRT, PRT		X			X		X	
Caffeine, Nicotine, Alcohol & sleep day of intake		X	X		X	X	X	X
Urine Pregnancy Test; PEERS (female only)			X (pre)			X (pre)		X (pre)
CGI-I, % homework tasks completed				X			X	
MID			X 			X		X
fMRI			X 			X		X
MRI checklist			X			X		X
Urine Drug Screen		X**						
Acceptability Questionnaire							X	

Between 8-15 weeks of therapy sessions (therapy will be either MBCT or BATA), in-person or remote during COVID-19 guidelines.

At visits week 4, 8 & 12 (if applicable), subjects will complete EEfRT & PRT computer tasks at the beginning of the visit followed by the therapy session or if during COVID-19 times, at a separate in-person visit from the remote therapy session. All paperwork done at therapy visits will be done in addition to procedures noted in this column. They will then complete the REDCap questionnaires at these key assessment time points (either in-person or done remotely by REDCap survey invitation). If the final therapy visit is before week 8, there will be three assessment points (pre-treatment, week 4, and at the last therapy visit). If the final therapy visit is between week 8 and week 12, there will be four assessment points (pre-treatment, week 4, week 8, and at the last therapy visit). If the final therapy visit is after week 12, there will be five assessment points, and post-treatment assessments will be administered either at the last therapy session or separately if therapy was remote. COVID-19

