For included participants, the subject will then complete the two computer reward tasks next because fatigue can affect their performance. Thus it is important to complete these tasks as soon as eligibility is confirmed.

- The Effort Expenditure for Rewards Task (EEfRT). The EEfRT is a computer task that takes 20 minutes and indexes the willingness to work for rewards under varying conditions of reward probability and magnitude. On each trial, participants simply select whether they wish to do an easy task (pressing a key 10 times with their dominant index finger) for a relatively smaller reward or a slightly harder task (pressing a key 100 times with their non-dominant finger) for a relatively larger reward.
- The Probabilistic Reward Task (PRT). The PRT is a computer-task that takes 20 minutes that is sensitive to behavioral shifts driven by reward in anhedonic patients. One of two reward-based responses receives feedback more frequently; this asymmetry typically induces bias toward the more frequently rewarded response. (COVID-19: Computers tasks will be done at the 2nd visit, which is in-person with an additional completion of another CSSRS at the end of the tasks, only after determining eligibility). COVID-19

Update:\*\*Please note that the conduct of the computer tasks with additional CSSRS at the in-person assessment visit and the urine drug screen are contingent upon the building availability and approval of in-person visits either at Duke or UNC. If not available and approved, the computer tasks with CSSRS and urine drug screen in person visit will be omitted until the study team have the appropriate approvals to do the tasks at an in-person visit. These omissions will not be considered protocol deviations since the omissions are necessary to be able to open the study and begin to collect the main primary outcomes of imaging and therapy. **NCE June 2022-tasks will only be done at Duke. Enrollment to UNC procedures is ending.**

3) *REDCap Self-report Questionnaires*

- a) Demographic Data Survey (DDS)
- b) PhenX Toolkit Core Tier 1 Impairment measures related to depressed mood
- c) PhenX Toolkit Core Tier 2 measures of perceived stress and life events
- d) The Beck Depression Inventory II (BDI-II)
- e) The Beck Anxiety Inventory (BAI)
- f) The Penn State Worry Questionnaire (PSWQ)
- g) The PTSD Checklist for DSM5 (PCL-5)
- h) Short Form-36 Health Survey, a widely used metric of quality of life
- i) Childhood Trauma Questionnaire (CTQ)

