## 6 STUDY INTERVENTION

### 6.1 STUDY INTERVENTION(S) ADMINISTRATION

#### 6.1.1 STUDY INTERVENTION DESCRIPTION

##### **Behavioral Activation Treatment for Anhedonia (BATA)**

Treatment in the R61 phase (Phase I) will consist of up to 15 weekly 45-minute sessions. This duration maybe modified in the R33 phase as a result of R61 phase Aim 2 analyses. Update for R33: Duration will remain as 8-15 weeks of treatment. Session 1 provides orientation and psychoeducation on anhedonia, and activity monitoring is introduced. Sessions 2-3 include structured values assessments of 10 life areas (e.g., Family Relationships, Employment/Career) to enhance motivation for sustained behavior change and to clarify goals. Following goals clarification, an activity hierarchy is developed, establishing a set of idiographic behavioral targets across life areas prioritized by ease of implementation to scaffold task engagement during the course of treatment. Session 4 focuses on reduction of avoidance. Sessions 5 and above assess completion of goals from the previous sessions, troubleshoot barriers to goal completion, and assign goals for the coming weeks. In the R33 phase, the minimum number of sessions will be 8 to allow for all planned content to be introduced, with a maximum of 15 sessions. Inherent in this structure is therapist assistance in setting achievable goals, which is often impaired in the context of anhedonia. Embedded in the review of goal completion is heightened awareness of anhedonia and identification of behaviors that are associated with greater positive response in the form of subjective importance and enjoyment. Those behaviors then form the basis of goals for the following weeks. The therapist uses motivational techniques to elicit goal-directed behaviors outside session including tying goals to the patient's identified values, open-ended questioning and reflective listening, and functional analysis to select behaviors maximally likely to achieve the patient's goals. Increased positive affect and decreased negative affect are theorized to result from increased contact with potential reinforcers through reduced behavioral avoidance. Maladaptive behaviors such as avoidance decrease the effectiveness of positive events in shaping future behavior, weakening the learned association between adaptive behaviors and positive outcomes. In this way, the overarching goal of BATA is to encourage the

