### **Mindfulness Based Cognitive Therapy (MBCT)**

Mindfulness is nonjudgmentally bringing awareness and acceptance to one's present-moment experience. Mindfulness-based interventions have demonstrated efficacy for treatment of diverse psychological symptoms including depression. To control for nonspecific factors in BATA including clinician contact, MBCT will be administered in an individual format. MBCT for individual treatment is empirically supported for a number of forms of psychopathology. Individualized adaptations of MBCT share primary components of the traditional program, including instruction and in-session practice of meditative exercises, didactics, and home practice. MBCT will be comprised of approximately 15 weekly 45-minute sessions. In the R33 phase, the number of sessions will match that of BATA. Sessions will begin with practice and discussion of a mindfulness meditation exercise, and then include: discussion of home practice, introduction to a new exercise and/or psychoeducational topic, and explanation of home practice for the coming week. Initial sessions will focus on practice and discussion of core meditation exercises to build mindfulness skills. Later sessions will focus on generalizing learned skills to cope with stressors and mood shifts. Psychoeducational content will center on identifying connections between negative thoughts, emotions, and sensations, recognizing triggers of emotional events, and developing an "action plan" to reduce stress-related symptoms. At the end of each session, participants will receive handouts that summarize the meditative exercise and/or psychoeducational content covered each week. Participants will also be asked to practice meditation exercises at home for 30 minutes each day and track practice time. Homework and logging are included to control for homework and monitoring components of BATA. Participants will receive guided meditation CDs (based on Segal et al.) to aid in home practice. Adherence will be monitored by tracking attendance; compliance of home practice will be monitored by evaluating frequency and duration of practice on weekly homework logs.

---

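### Section 4.2 lets the PRT and EEfRT follow a therapy session although the schedule puts them first, so some post-treatment task measurements can carry an acute session effect that baseline never has

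*Combined protocol and SAP*

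**What the plan says.** Three places govern when the tasks are done relative to therapy.

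- Section 1.3, footnote 2, for weeks 4, 8 and 12: "subjects will complete EEfRT & PRT computer tasks at the beginning of the visit followed by the therapy session", or at a separate in-person visit when therapy is remote during COVID-19.
- Section 4.2, Treatment, for the same weeks: "The subject may have their therapy session before or after these tasks & surveys or may be completed on a separate day".
- Section 4.2, final therapy visit: the tasks are repeated "At the final therapy visit (anytime between 8-15 weeks as determined by Duke/UNC study team) or separately", with no statement of whether they precede or follow the session.

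The synopsis lists the PRT and EEfRT among the primary endpoints, and they carry Aim 4. Baseline tasks belong to the screening assessment, before randomization; once eligible, participants "complete the two computer reward tasks next because fatigue can affect their performance". The Aim 3 and 4 model in Section 9.2 uses two time points, pre- and post-treatment, and adjusts for gender and age. No section says that the order of tasks and therapy is recorded or analysed.

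**The concern.** Aim 4 asks whether a course of BATA changes reward sensitivity more than a course of MBCT does. A task done minutes after a session may also reflect the state that the session has just produced. The sessions differ by design. In BATA, "The therapist uses motivational techniques to elicit goal-directed behaviors outside session"; in MBCT, "Sessions will begin with practice and discussion of a mindfulness meditation exercise". The EEfRT measures willingness to work for reward and the PRT measures bias driven by reward, so an acute effect that differs by arm is plausible, though nothing in the documents demonstrates one.

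The protocol takes care over acute state elsewhere. Section 4.2 asks participants to avoid nicotine and caffeine for 2 hours before the tasks, alcohol on the day and THC for 24 hours, and it records recent intake and sleep at task visits. Leaving open whether a session of 45 minutes to an hour comes immediately before the tasks does not fit with that care.

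**Working it through.** **Do the passages conflict?** Yes, for weeks 4, 8 and 12. Footnote 2 puts the tasks first; Section 4.2 allows either order or another day. Both are current text. A task done after that day's session complies with Section 4.2 and breaches footnote 2.

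**Does this reach the analysed contrast?** In part. The Aim 4 model uses only pre- and post-treatment data, so a mid-treatment measurement does not enter it. There are two routes in:

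1. Sections 6.1.2 and 6.4 allow therapy to be declared complete from week 8. If week 8 or 12 is the last session, the either-order sentence governs the post-treatment measurement.
2. At any other in-person final visit there is no contradiction, but there is no rule either.

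**Who is not exposed?** Participants whose tasks are at a visit separate from remote therapy (footnote 2), on a separate day, or at UNC (allowed for the final tasks, and the stated route for those who leave before week 8). Omitted tasks contribute no measurement.

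**What would the bias be?** Let q be the share of an arm's post-treatment tasks done after a session and a the acute effect in SD units, with subscripts B (BATA) and M (MBCT).

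- Bias in the between-arm difference in change = q_B × a_B − q_M × a_M.
- Same order pattern in both arms: q × d, where d = a_B − a_M. With d = 0 there is no bias between arms, only added noise and a shift from baseline common to both.
- Same acute effect a in both arms: a × (q_B − q_M).

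The documents give no value for any of these terms.

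**Illustration of scale.** The only usable design inputs are in Section 9.1, and they are stated for the SHAPS: 65 completers per arm and a correlation of 0.35 between assessments.

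The plan's own figures were reproduced first, using λ = f² × N × m / (1 − ρ), N = 130, m = 2 and F(1, 128):

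- f = 0.20: λ = 0.04 × 260 / 0.65 = 16.0, power 97.8% (stated 98%).
- f = 0.14: λ = 0.0196 × 260 / 0.65 = 7.84, power 79.4% (stated 80%).

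Applying the same n and correlation to a task score with unit SD at both times:

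- SE of the difference in change = √(2 × (1 − 0.35)) × √(2/65) = 1.140 × 0.1754 = 0.20 SD.
- The true size of a nominal 5% test follows from noncentrality (q × d / 0.20)².

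With assumed q and d:

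- q = 0.25, d = 0.1: bias 0.025 SD, type I error 5.2%.
- q = 0.5, d = 0.2: bias 0.10 SD, type I error 7.9%.
- q = 0.5, d = 0.3: bias 0.15 SD, type I error 11.5%.
- q = 1, d = 0.3: bias 0.30 SD, type I error 31.9%. This is an extreme, since the documents provide for separated task visits.

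The direction is unknown.

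**The case against.** The strongest reply is that this is a wording inconsistency with an unquantified mechanism attached. Much of it stands.

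- The direct contradiction covers weeks 4, 8 and 12, and most of those measurements never enter the Aim 4 contrast. Carrying the tasks-first order to the final visit extends footnote 2; it does not merely enforce it.
- Remote therapy, separate-day visits and UNC visits remove the exposure. The exposed share could be small, particularly in the remote period.
- Both arms have the same freedom of order. The documents do not show that order differs by arm.
- The fatigue remark concerns doing the tasks promptly at screening. Fatigue after a session of similar length in each arm would largely cancel between arms, so it does not support an arm-specific effect.
- The protocol version is dated October 2023, after imaging enrolment closed in June 2022, so a prospective rule may help few participants.

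What does not fall is the core: two primary-listed outcomes can be taken under a condition that baseline never has and that varies between participants. The analysis plan does not address it.

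A reader might infer that the Aim 4 comparison is biased by a definite amount. For example, exposed shares of 25–75% and acute differences of 0.1–0.3 SD would give 0.25 × 0.1 = 0.025 to 0.75 × 0.3 = 0.225 SD. The documents do not support that reading. Every input is assumed, the shares ignore the separated visits, and zero is equally compatible with the text.

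**Conclusion.** The conflict between footnote 2 and Section 4.2 is real, and the final-visit text leaves the order open. As a result the PRT and EEfRT can follow an arm-specific session at some post-treatment assessments, while baseline tasks never do. For exposed participants, within-arm change from baseline is open to an acute effect whatever the arm. The BATA–MBCT contrast is biased only if the acute effect or the order differs by arm.

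The size is unknown. The illustration runs from negligible to material, and it rests on assumed exposure and acute effects and on borrowing the SHAPS sample size and correlation for the task scores. The point justifies an inexpensive correction; it does not show that Aim 4 is invalid.

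**What to change.** - **Protocol text.** Reconcile footnote 2 of Section 1.3 with the Treatment and final-visit text of Section 4.2. At weeks 4, 8 and 12 and at the final visit, have the EEfRT and PRT done before that day's session or on a day without therapy.
- **Recording.** At each task visit, record whether the tasks came before a session, after a session or on a separate day.
- **Data already collected.** No section says that order was captured, so first establish whether it can be recovered. Where it can, tabulate order by arm at post-treatment, then report an Aim 4 sensitivity analysis with post-treatment order and an order-by-arm term.
- **Do not rely on exclusion.** Dropping tasks done after a session conditions on a post-randomization variable and can introduce selection if order differs by arm. The order model keeps all participants in the analysis, but order is post-randomization there too, so its result should be read as descriptive.
- **SHAPS.** Leave its timing alone. Section 4.2 sets it at the end of each therapy visit, and moving it would change how a repeated outcome is administered mid-trial.

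The cost is slightly less scheduling freedom, one recorded variable and one sensitivity analysis.
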